The study screening and research procedures will take place at the patient's home or in the health education office, or another Sea mar Clinic location, per patient preference. If possible, the visit will be performed in person, but given the increase in tele-health visits during the COVID pandemic, if a potential participant is unable to complete the screening visit and/or research visits in person, then tele-visits for the research visits will be offered.

Population:

We propose to perform an observational prospective study that will involve 100 subjects with confirmed type 2 Diabetes. There will be 50 participants in the RT-CGM+education intervention group and 50 in blinded-CGM+education group. Patients with type 1 diabetes as well as controlled diabetes <8.0 % will be excluded (8.0 or greater included). Sea Mar clinics care for more than 8,500 patients living with diabetes, and when the designated clinics were reviewed for Latinx patients with A1C ≥8.0%, over 460 potential participants were found. Thus, we will have a robust population for recruitment and diabetes self-empowerment. Additionally, participants may be found in the local community or UW clinics

E. Statistical Considerations

Sample Size Estimation

In this study, we plan to enroll and include a total of n=100 study participants. The study is designed and sized first for assessing the primary endpoint of change in A1C from baseline to 12 weeks (Aim 1), and secondarily to assess the impact of RT-CGM on A1C. To assess statistical power, we assumed a standard deviation in baseline A1C of 1.2 and a reduced standard deviation of 1.0 at 12 weeks to reflect an anticipated reduction in A1C due to the *Compañeros en Salud* curriculum. We further assume a correlation in A1C measurements of $r=0.5$, which is likely to be higher and will result in greater statistical power. Finally, assuming a 15% reduction in the effect sample size (n=85) due to attrition, the study is sized to detect reductions in A1C of 0.4 or larger with 90% statistical power. If the actual correlation between baseline and week 12 HbA1c measurements is $r=0.7$ or higher, the study has 90% power to detect differences in A1C as small as 0.3. Under similar assumptions, the study is sized to detect a 0.6 difference in 12-week HbA1c between subjects randomized to RT-CGM vs blinded CGM (power = 0.82 assuming $r=0.5$; power=0.93 assuming $r=0.7$). A two-sided type 1 error rate of 0.05 was assumed throughout.

Data Analysis Plan

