Randomization. The study biostatistician will generate a randomized sequence of treatment group assignments using stratified permuted-block randomization (random block sizes of 2, 4, 6) stratified by A1C >9.0% and ≤9.0%. Sequences will be stored at and delivered through the REDCAP study database at the UW. Research staff will obtain the next randomization once a potential study participant has been determined to be eligible and has signed the study consent form.

Vital signs, anthropometrics measurements, and demographic information will be collected, and participants will be asked to complete study surveys as further detailed below. Participants will be asked to use pedometers and keep them on their person as much as possible during waking hours. Baseline data will be collected no more than 3 weeks prior to the initiation of the DSMES curriculum, and pedometer data will be collected over 10 days immediately following the baseline study visit. Both groups will undergo blinded CGM with insertion by study personnel over the same 10 days following the baseline visit. Participants will then have a follow up visit from a Patient Navigator 10-14 days after the initial visit (detailed below) If less than 72 hours of CGM data is obtained at follow up PN visit participants will be asked to repeat blinded CGM. Participants will be asked to continue their customary dietary and exercise habits until initiation of the intervention

Follow-up study visits given in a community setting will be within an acceptable window for data collection and held at weeks 12+/-2 weeks and 24+/-2 weeks (Visits 2: end of education intervention and visit 3:12 weeks after education intervention. The same procedures will be completed as described in detail below. Visits 2 and 3 also may be held in the participant's home or Sea Mar clinic according to the participant's preference and be completed through a remote RC visit with a PN in person visit to complete blood pressure, weight circumference and weight and A1c. The study team will continue to contact withdrawn participants to conduct an interview regarding barriers to study engagement.

Study Procedures

The following procedures will be performed at baseline (visit 1), (Visit 2) and (Visit 3):

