Anthropometric and vital sign measurements: **Height** will be measured by a Stadiometer. **Weight** will be measured using a SECA Digital scale, and BMI (kg/m^2) will be calculated. **Waist circumference** will be measured using a flexible measuring tape. Participants will remain in a seated position for a minimum of 15 minutes prior to measurement of **resting heart rate** and **blood pressure** with an Omron Professional Digital blood pressure and heart rate monitor.

Concomitant medications: Participants will be instructed to bring all current medications (prescription, over the counter, and herbal or vitamin supplements) to each study visit. The research study coordinator will review and record these medications. Comorbidities: We will use patient self-report to document stroke, CVD (congestive heart failure, myocardial infarction, or coronary heart disease), peripheral vascular disease, peripheral neuropathy, renal disease, and retinopathy. Point of Care A1C: The DCA Vantage Analyzer tests for a quantitative determination of A1C in human whole blood and provides immediate test results from a finger prick of blood. If age <50 and female urine dipstick for pregnancy completed.

Pedometer: participants will be given a pedometer or if preferred use the one available on their smartphone. They will be asked to keep the pedometer or phone on them as much as possible during waking hours during the study. Data will be collected for 10 days after the first visit then for the 10 days prior for visits 2 and 3.

Continuous Glucose Monitoring:

Blinded CGM: All participants will undergo blinded CGM for 10 days at baseline a (2-4 weeks prior to start of education) and visit 3 (24 weeks [+/-2 weeks]). The blinded CGM- education group will also complete blinded CGM for 10-day period at the end of the education intervention (visit 2: study weeks12 [+/-2 weeks]). Participants can mail blinded CGM devices back in self-addressed postage-paid envelopes provided at the initial PN visit and devices will be provided at the first PN visit.

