RT-CGM: Participants in the RT-CGM arm will be asked to wear the device for a total of 50 days for 84 days during the 12 weeks of education sessions at intervals of 10 days on then 7 days off over 12 weeks. CGM data for 10 days will be downloaded after the completion of the 3rd RT-CGM wear session which should correlate approximately with the 6th education session. The final period of RT-CGM use will begin on the day of the final session of the DSMES curriculum. Participants will undergo initial training by PN and can have assistance for the first device self-insertion and may request additional virtual, telephone, or in-person assistance from PN. In our experience, study participants readily assimilate the self-insertion technique and require negligible follow-up support for this procedure. RT-CGM data will be collected remotely using a cloud-based platform

Preparation for the study intervention: Patient Navigators (PN) from Sea mar health education team will engage participants no more than 2-4 weeks prior to the start of the DSMES intervention to ensure participants have a working technology platform for the education sessions and provide hot spot if able through one home visit with option for second if need to assess barriers to technology or attendance. For all participants, PN will teach simple CGM insertion (blinded and RT). For those who are enrolled in RT-CGM arm, the PN will set up a mobile app for the RT-CGM device. PN also will conduct a 1, 30-minute training session on CGM for participants in this study, with particular focus on the use of RT-CGM as a tool to understand food and activity choices. If RC is remote PN may also engage at visits 1, 2 and 3 to gather objective measurements (weight, blood pressure and POC A1C or participant may go to LabCorp/quest for the A1C) As well they well gather the 10 days baseline pedometer data

Study Procedures: Study Participants' Household Member: No protected health information will be recorded for household member. Demographics of relationship to study participant, age and sex and history of diabetes or prediabetes will be recorded at baseline visit. Email address maybe recorded in order to contact patients if verbal permission is given.

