- For app users, the "Share and Follow" functionality will be discussed and encouraged (i.e., the study participants are able to invite followers to review their glucose levels).

Control/ Blinded-CGM-Education group

The participants of the control group will perform self-monitored blood glucose testing as indicated by their primary care provider with blood glucose meter as per typical care provided by their healthcare system.

At completion of study, 30 control group participants who express interest verbally will be given 3 Dexcom Real Time sensors. Data collected from these sensors will not be used for study activities. Participants will be made aware that they are responsible for reporting all glucose values collected by these devices to their Seamar clinical team.

RT-CGM Handout:

A simple educational handout has been developed to explain glucose goals and also how food and activity affects blood sugars. This handout will be reviewed with RT-CGM participants at PN visit(see Appendix A) and Appendix A2 for those not using RT-CGM

K .Measurements (Appendix B):We will measure A1C at the beginning of the study period visit 1 weeks and A1C at visit 2 and A1C and visit 3. At each visit, blood pressure, resting heart rate, weight and height will be measured. For blood pressure and heart rate two values will be taken and the average used. At baseline and visit 2 and 3 , questionnaires on diet and physical activity and personal wellness questionnaires will be obtained. In the intervention group at visit 2 , a questionnaire about CGM technology and perception of benefit of CGM use will be obtained.

Anthropometrics: **Height** will be recorded in centimeters and inches by a stadiometer. **Weight** will be recorded in pounds and kilograms using a Digital scale. Two measurements will be taken, and the average will be used. **Blood pressure and pulse** are taken with an Professional Digital blood pressure machine. Two measurements will be obtained at each appointment. If performed via remote

televisit then patients will use their own blood pressure cuff and available scale. **Waist measurement** will be measured using a flexible tape measurer.

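### Weight and blood pressure at remote visits have two measurement routes with no stated order, so a device switch can enter the secondary change scores

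*Combined protocol and SAP*

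**What the plan says.** All references are to the combined protocol and SAP.

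- **Standard equipment.** Under Study Procedures in Section H, weight "will be measured using a SECA Digital scale, and BMI" is derived from it. Blood pressure is taken "with an Omron Professional Digital blood pressure and heart rate monitor". Height is by stadiometer.
- **When visits go remote.** Section D says that if a participant cannot attend in person, "then tele-visits for the research visits will be offered". The Televisits paragraph of Section J also prefers in-person visits and allows telehealth when they are not possible.
- **Remote route 1: the Patient Navigator (PN).** Section H says visits 2 and 3 may "be completed through a remote RC visit with a PN in person visit to complete blood pressure, weight circumference and weight and A1c". The paragraph on preparing for the intervention adds that, with a remote coordinator, the "PN may also engage at visits 1, 2 and 3 to gather objective measurements".
- **Remote route 2: the participant's own devices.** Section K first repeats the stadiometer, digital scale and professional monitor. It then says that at a remote "televisit then patients will use their own blood pressure cuff and available scale".
- **Height.** Section K also says: "At each visit, blood pressure, resting heart rate, weight and height will be measured". It does not say which height is used to calculate BMI.
- **Analysis.** Section E, Aim 1, makes change in weight, BMI and blood pressure at 12 and 24 weeks secondary outcomes. The A1C model has fixed effects for RT-CGM and time, and secondary outcomes follow the same approach. The plan describes no term for visit mode or device.

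**The concern.** Visit mode can change from one visit to the next, so a participant can be weighed on the study scale at baseline and on a bathroom scale at week 12. The difference between the two scales then counts as weight change for that person. The same holds for blood pressure and, through weight, for BMI.

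This matters most for the whole-cohort change. Aim 1 inference centres on change in all participants regardless of RT-CGM status, and the secondary outcomes are handled similarly. That change has no concurrent control, so randomization does not protect it from a shift in how readings are taken. The effects sought may also be modest: the 15-person pilot in Section C reports an average loss of five pounds. If device and mode are not recorded, no later analysis can separate the two sources of change.

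**Working it through.** **The two remote routes side by side**

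| | PN route (Section H) | Own-device route (Section K) |
|---|---|---|
| Trigger | Coordinator is remote | Visit is a remote televisit |
| Visits covered | 2 and 3 in one place, 1 to 3 in another | Not limited |
| Force | Permissive (may) | Directive (will) |
| Who measures | Navigator, in person | Participant |

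A remote coordinator visit meets both triggers. No sentence ranks the routes, and none asks for the same device across a participant's visits. A1C, by contrast, has an order for remote visits in Section L: the community health worker if possible, otherwise an outside laboratory.

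**How a switch enters the change score**

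The documents give no SD, effect size, power or remote-visit share for weight or blood pressure, so there is no planned figure to reproduce. Let f be the share of participants who move from study to own device after baseline, b the mean offset (own minus study), and s the SD of the offsets.

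- Bias in whole-cohort mean change = f × b. Switches in the opposite direction subtract.
- Bias in the between-arm difference = (f₁ − f₀) × b, which is zero when switching is equal in the two arms.
- Variance of change rises by about f × s².
- A participant who stays on one home device has a constant offset, which cancels.

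**Illustration with assumed values (none is in the documents)**

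- Weight, b = 1 to 2 kg and f = 10% to 30%: from 0.1 × 1 = 0.1 kg to 0.3 × 2 = 0.6 kg. Against the pilot's five pounds (2.27 kg) that is 4% to 26%.
- Blood pressure, b = 1 to 5 mmHg and f = 10% to 50%: from 0.1 × 1 = 0.1 mmHg to 0.5 × 5 = 2.5 mmHg.
- Between-arm, same b, switching shares 10 to 20 points apart: from 0.1 × 1 = 0.1 mmHg to 0.2 × 5 = 1.0 mmHg.
- Noise, change SD 10 to 15 mmHg, s = 3 to 8 mmHg, f = 10% to 50%: at the low end √(15² + 0.1 × 3²)/15 = 1.002; at the high end √(10² + 0.5 × 8²)/10 = 1.149. The SD rises by 0.2% to 15%.

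**Height and BMI (assumed person: 80 kg, 160 cm)**

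- 80/1.60² = 31.25 and 80/1.61² = 30.86, so a 1 cm height error at one visit moves BMI by 0.39 kg/m².
- For scale, a 2.27 kg loss moves BMI by 2.27/1.60² = 0.89 kg/m².
- With one fixed height, the same 1 cm error changes that BMI loss only from 0.89 to 2.27/1.61² = 0.88 kg/m².
- Independent errors largely average out. With an error SD of 1 cm at each of two visits and n = 100, the added standard error is 0.39 × √2/√100 = 0.055 kg/m².

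**The case against.** The strongest reply is that the passages fit together as a fallback order: in person first, then a remote coordinator with a Navigator on site, then own devices for a fully remote visit. The Navigator provisions are permissive, so a reader who infers a flat contradiction goes further than the text allows. That stands. But the protocol never states the order, and even under this reading a participant can change device between visits.

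A reader might also take the illustrated 0.1 to 0.6 kg as the expected bias. The documents do not support that. It needs home scales of different makes to err in the same direction, plus a switching share that is nowhere given. With mixed signs the effect is mainly noise.

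Nor do the documents support inferring that the randomized comparison is biased. The remote provisions are the same for both arms, and no mechanism for unequal switching appears.

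On height, setting one person's 0.39 kg/m² beside a mean effect of 0.89 kg/m² could suggest bias of similar size. As the standard error above shows, the group-level effect is mainly a little extra noise.

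It may seem natural to exclude own-device values from the main analysis. That could remove data selectively from people who cannot attend, on top of the 15% attrition already assumed in Section E. This objection stands, and the fix keeps those values.

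Finally, the measurement table (Appendix B) and visit form (Appendix M) are listed but not available here, so they may already record device or mode.

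**Conclusion.** The point holds as an unreconciled pair of procedures with a possible effect on secondary outcomes. The current text gives no order between Navigator and own-device measurement and does not require the same device across visits, so a device difference can enter weight, BMI and blood pressure change. The whole-cohort change is biased if the mean offset is non-zero and switches do not balance; otherwise precision is lost. The between-arm contrast is biased only if switching differs by arm. The own-device sentence does not concern A1C, so the primary endpoint and its sizing are unaffected.

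The size cannot be determined from the documents, and every figure for device bias or noise above rests on assumed inputs. The BMI arithmetic is exact for the assumed person, but the 1 cm error is itself an assumption. The changes are worth making because they are cheap and because an unrecorded device cannot be recovered later.

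**What to change.** 1. In Section K, replace the own-device sentence with an order. When the coordinator is remote, Navigator measurement of weight and blood pressure with study equipment is the first choice. The participant's own cuff and scale are the fallback only when that is not possible. Align the two Section H paragraphs with this wording.
2. Record device and visit mode in REDCap at each visit, unless the visit form already does so.
3. Keep own-device values, flagged, in the main analysis. Add a sensitivity analysis in Section E limited to study-device measurements.
4. Calculate BMI at all visits from the baseline stadiometer height. Re-measurement error then stays out of BMI change, and a remote follow-up visit needs no stadiometer. If the baseline visit is itself remote, name the in-person contact that supplies this height.

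The cost is somewhat more use of Navigator visits that the protocol already allows, one added data field, and one added sensitivity analysis. The BMI rule costs nothing beyond wording.

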Aim 1: Determine the impact of the *Compañeros en Salud* (Partners in Health) curriculum in conjunction with RT-CGM on glycemic control in Latinx patients with T2D. We will enroll 100 Latinx patients with uncontrolled T2D through a federally funded healthcare network across the Seattle region. Participants will be randomized to receive the *Compañeros en Salud* diabetes self-management education and support (DSMES) intervention with or without RT-CGM (n=50 per group) over 12 weeks with an additional 12 weeks of follow-up.(control= blinded -CGM+ Education and intervention= RT-CGM + education). Study visits will be held at screening, baseline(0-4 weeks) and 12 weeks (+/- 2 weeks) and 24 weeks (+/-2) weeks. Participants in the blinded -CGM+ Education group will undergo blinded CGM for 1 week at baseline and for 10 days after each study visit. The primary outcome will be A1C. Secondary outcomes will include time in range as measured by CGM and other CGM indices, body mass index, waist circumference, and systolic and diastolic blood pressure.

Aim 2: Engage key stakeholders to optimize acceptability and minimize barriers to participation in the intervention. After 25% of participants have completed the intervention, we will convene a committee of stakeholders that includes study participants (both completers and non-completers), community providers, diabetes educators, and patient navigators. Key barriers and facilitators to the intervention will be identified by stakeholders, and the intervention will be amended based on stakeholder feedback. The impact of these revisions on participant engagement during the study intervention will be analyzed.

Aim 3. Determine the effects of the *Compañeros en Salud* curriculum with or without adjunct RT-CGM on diabetes-related behaviors and distress. At baseline and 12-+2 weeks and 24 +/- 2 weeks, participants will complete surveys capturing dietary behaviors, physical activity, and diabetes-related distress. Participants will be provided with pedometers, and activity data will be captured for 10 days following each study visit. **Sub-aim 3A:** As an exploratory sub-aim, we will examine behavioral changes in other members of participants' households through brief surveys. This sub-aim will provide preliminary data regarding a possible "ripple effect," the capacity for an intervention in 1 individual to affect health-related behaviors in other household members.

B. Background

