CGM (DEXCOM G6): A continuous glucose monitor (CGM) is a way to measure glucose levels in real-time throughout the day and night. A tiny electrode called a glucose sensor is inserted under the skin by a skin prick to measure glucose levels in tissue fluid. A small plastic piece of tubing remains inserted in the skin. Typically, one cannot feel this tubing once inserted. It is connected to a transmitter that sits on top of the skin and is about the size of a quarter. It is attached or secured by medical tape to the wearer's skin. It is approved for use on the abdomen and has been shown to be effective for use on alternative sites such as upper buttock and arm for 10 days. The CGM either records the blood sugars and stores which we will then be mailed or returned at education session one or it sends the information via wireless radio frequency to a monitoring/display device or to a cellular phone so one can see their own data on their glucose, and we can download it remotely. The device automatically generates an alert for glucose < 55, and an alert will also be generated for glucose > 180 in the unblinded portion of the study. The intervention group participants will be given a handout (Appendix K) for troubleshooting these alerts, particularly during the blinded portion of the study. DEXCOM G6 is FDA approved for use in patients with diabetes and will be used in accordance with instructions as approved for diabetes. The risk is minimal with use of this device. In this study, we recommend patients connect the CGM to their cell phones. Study staff will insert the first sensor for the groups and then PN at digital navigation visit will demonstrate how to insert additional sensors for the intervention group who will continue to use RT-CGM and control group in case they need to self-insert blinded CGM. If this is to be done as a televisit, the sensors, transmitter, and device (if needed) will be mailed to the participant. Then the study staff will walk the participant through the first insertion through a virtual zoom visit. Patients will also have a YouTube video available for reference for the patients. The patients will be instructed on how to remove the sensor themselves after 10 days and bring it back or mail back. The RT-CGM-education intervention group will wear the RT-CGM- cyclically and have telephone support and may refer to the YouTube video on insertion if needed. The intervention participants will have RT-CGM download after 3 cyclic sessions of use and at 5 sessions of use. The Blinded-CGM education group participants will wear the blinded CGM at baseline and 24=/- weeks at conclusion of intervention. If, during the blinded portion of the study, due to device malfunction (rather than subject non-compliance), the device records less than 3 days of data, the participant will restart another 10 days of blinded CGM data.

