
The receiver and/or the app will display the glucose reading along with a rate of change arrow and a trend graph. Additionally, the receiver and/or app issues alarms and alerts to notify the patient of glucose level changes and other important system conditions. The app provides the additional capability to share data with "followers" using the Dexcom Share service.

CGM Ancillary Devices Dexcom CLARITY® is an accessory for users of the Dexcom CGM system. It is a software program that allows the transfer of glucose data from the CGM system to Dexcom remote servers for data management to allow the use of the CGM data by the user and study clinicians. Target ranges of 70 to 180 mg/dl will be set, and the patients will be introduced to the use of alarm settings. Both participants and study sites will use CLARITY® to transfer glucose data between user and study site, whether CGM is used in blinded or real-time mode. A CLARITY® mobile app can be used for a retrospective review of glucose data on the smart device and can also be set up to allow receipt of push notifications of CGM data facilitating data review. For all patients (intervention and control group) an anonymized CLARITY® account will be created by using a sequential study number which is allocated at randomization. Additionally, if participants desire The Dexcom G6 CGM System comes with a built-in Dexcom Share feature so you can let up to 10 people follow your glucose levels,

giving you a circle of support. By downloading the Dexcom Follow app, Followers can view your glucose data directly from their smart device

Intervention/ RT-CGM- education Group:

- For participants the DEXCOM G6 CGM app will be installed on participant's smart phone.
- An anonymized CLARITY® mobile account will be set up and linked to the research site.
- A high alert threshold will be set at 180 mg/dl and low alert threshold for <70mg/dl. In addition, the urgent low alert (55 mg/dl [3.1 mmol/l]), the urgent low soon alert (when glucose levels are falling fast and will be below 55 mg/dl [3.1 mmol/l] in less than 20 min) as well as alerts for rise and fall rate (3 mg/dl [0.17 mmol/l]) in addition to alerts for signal loss and no readings for more than 20 min will be enabled and patients will be shown how to turn off if they desire.
- Participants with applicable smart phones may have CLARITY® push notifications on the CLARITY® mobile app about weekly time in range comparison enabled during the study.

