Pedometer data: Pedometers will be supplied to all participants at the baseline study visit or if preferred participants can use the step counting app embedded in their smart phone (Visit 1), and participants will be asked to wear the devices or keep their phone on them as often as possible during waking active hours. Data will be downloaded by PN in the participants' homes 10 days after the baseline, and for the 10 day prior to visit 2 and visit 3 -week. We will compare average steps per day over the 10-day period prior to visit 2 and visit 3 relative to baseline steps.

L. Collection of Human Biological Specimens:

Fingerstick and serum A1C: The HbA1c test is a blood test that provides information about a person's average levels of blood glucose over the last 3 months. The DCA Vantage Analyzer HbA1c assay tests for a quantitative determination of HbA1c in human whole blood, and provides immediate test results from a finger prick of blood. If remote visit is completed and CHW can not complete A1C then participant maybe asked to go to Labcorp to A1C measurement

Dip Stick urine test: Dipstick urine test will be completed at screening if indicated with immediate results available to review or if needed can be completed at Labcorp

M: Questionnaires : All questionnaires will be available in REDCAP and completed at time of baseline visit with RC in person or remotely. For visit 2 and 3 Redcap surveys will be sent in advance and can be completed by participants in advance and then reviewed with RC or if not completed in advance completed during visit 2 and 3. Assent for household members will be on top of Redcap survey or read to person if in person or on the phone (Appendix N)

Nutrition questionnaire: Starting the Conversation (STC) is an eight-item, simplified food frequency instrument designed and validated for use in primary care and health-promotion settings. It asks respondents to estimate the number of times they consumed certain types of foods over the past week, including fast food, fruits and vegetables, and sugared beverages. Importantly, it has been used and validated in diverse populations including Latinx individuals.⁶⁶ (appendix G). It will also be used for household members >12 years old.

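### Steps/day may be counted by pedometer or by the participant's own phone, and RT-CGM runs on the phone in one arm only, so phone-recorded steps at visit 2 could rise more in that arm without more walking.

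*Combined protocol and SAP*

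**What the plan says.** **Device.** The Pedometer paragraph of Section H (Study Procedures) says "participants will be given a pedometer or if preferred use the one available on their smartphone". Section K (Pedometer data) repeats the option: "or if preferred participants can use the step counting app embedded in their smart phone". The same section addresses everyone, regardless of arm: "participants will be asked to wear the devices or keep their phone on them as often as possible during waking active hours".

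**Window.** Section H collects steps for 10 days after visit 1 and for the 10 days before visits 2 and 3, and Section K agrees: "We will compare average steps per day over the 10-day period prior to visit 2 and visit 3 relative to baseline steps". The statement of Aim 3 at the front differs: "activity data will be captured for 10 days following each study visit".

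**Phone and CGM.** The baseline step window coincides with blinded CGM in both arms (Section H, under Randomization). After that, the Intervention/RT-CGM-education Group list states that the "DEXCOM G6 CGM app will be installed on" the participant's smartphone and that "alerts for signal loss and no readings for more than 20 min will be enabled". The same bullet adds that participants will be shown how to switch these alerts off. The control group monitors with a blood glucose meter. The Medical Devices text adds, without naming an arm: "In this study, we recommend patients connect the CGM to their cell phones".

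**Analysis.** Section E (Aims 3 and 3A) lists average steps/day first among the secondary outcomes. It codes the RT-CGM coefficient as the average difference in 12-week change. The one covariate it adds for Aim 3 is survey language. It names no term, stratification or sensitivity analysis for the step device.

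**The concern.** A phone counts steps only while it is carried. In the RT-CGM arm the phone is also the planned glucose display, and it sounds an alert when the sensor signal is lost. That is an added reason to keep it close, which control participants do not have between visits 1 and 2. If phone users in the RT-CGM arm carry the phone for a larger share of their walking than they did at baseline, recorded steps rise with no change in behavior. The rise enters the between-arm contrast directly, because baseline was recorded without the real-time display in either arm.

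This matters because Section C proposes behavior change as the route by which RT-CGM lowers glucose, and notes that the earlier trial did not capture activity. A recording artefact in favor of RT-CGM would look like the evidence the trial hopes to supply. If the device is neither fixed nor recorded, the artefact could not be separated out afterwards.

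The conflict over the window is a separate matter, but it affects which days, and how many RT-CGM days, enter the outcome.

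**Working it through.** The plan gives no power, SD or target difference for steps/day, so there is no stated figure to reproduce. Two checks apply.

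**1. Overlap of RT-CGM wear with the step window**

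Inputs: 10 days on and 7 off over 12 weeks, five wears, with the last starting on the day of the final class (Section H, RT-CGM; note under Figure 1). Assumption: first class and first wear on day 1.

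- Wears start every 17 days: days 1-10, 18-27, 35-44, 52-61 and 69-78, which is 50 days.
- The twelfth weekly class falls on day 1 + 11 × 7 = 78. Under the final-class rule the last wear is days 78-87 instead.
- For visit 2 on day 84, the preceding 10 days are days 74-83. Overlap with 69-78 is days 74-78, or 5 days. Overlap with 78-87 is days 78-83, or 6 days.
- Across the visit 2 dates checked within the ±2-week allowance (days 70, 77, 78, 84, 91 and 98), overlap runs from 0 to 9 days.
- At visit 3 (days 154, 168 and 182 checked), overlap is 0.
- With the window in the Aim 3 statement (days 85-94 after a day-84 visit), overlap is 0 or 3 days. The two windows therefore differ in RT-CGM exposure. They also differ in content: days 74-83 straddle the last class, while days 85-94 lie wholly after it.

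**2. Possible size**

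None of these inputs is in the documents. Assume 5,000 true steps/day, half of the RT-CGM arm using phones, and phone capture rising from 70% of steps to 80-90%, with control capture unchanged.

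- Phone user at baseline: 0.70 × 5,000 = 3,500 recorded.
- Phone user with RT-CGM: 0.80 × 5,000 = 4,000 (+14%) to 0.90 × 5,000 = 4,500 (+29%).
- Arm mean, if wear covered the whole window: 0.5 × 500 = 250 to 0.5 × 1,000 = 500 steps/day.
- At 5 of 10 days: 125 to 250. At 6 of 10 days: 150 to 300. Combined range: **125 to 300 steps/day**.

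Effect on a two-sided 5% test with no true difference in walking: SE = SD × √(2/42.5), taking 42.5 per arm from the plan's 85 evaluable participants and an assumed SD of change of 2,000 to 3,000. This gives SE = 434 to 651.

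| False difference (steps/day) | Rejection rate, SD 2,000 | Rejection rate, SD 3,000 |
|---|---|---|
| 125 | 6.0% | 5.4% |
| 300 | 10.6% | 7.5% |

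Wider assumptions, with wear covering the whole window, show how little the documents constrain the answer:

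- Low: 4,000 steps × 25% on phones × 5 points more capture = 50 steps/day (about 5.1% at SD 3,000).
- High: 8,000 × 75% × 20 points = 1,200 steps/day (79% at SD 2,000).

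**The case against.** The strongest reply is that the protocol already asks every participant, in either arm, to keep the pedometer or phone on them through waking hours. A reader might infer that only the RT-CGM arm has a reason to carry the phone. Sections H and K do not support that. Any artefact is what the app and alerts add beyond a shared instruction. This part of the reply stands and reduces the likely size, but it does not equalize the arms.

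Other points also stand:

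- The alerts can be switched off, and the device text mentions a receiver as an alternative display, although the plan for this arm is the app.
- The recommendation to connect the CGM to a phone names no arm. If blinded sensors were also linked at baseline, the RT-CGM arm might show little rise. Controls would then lose the prompt before visit 2, so the bias would keep the same direction.
- Only phone users are affected, and their share is unknown.
- Self-reported walking and the physical activity questionnaire do not depend on a phone. They are a partial check only, because they are self-reports under open allocation.
- Pedometers also count only when worn, so a pedometer rule does not remove every difference in compliance.

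A reader might also infer that participants will change device between visits. Section K places the choice at visit 1, and nothing provides for later switching; the text simply does not rule it out. Whether device type is recorded cannot be settled from the body text, since the measurement table and visit form are listed as appendices but their contents are not available here.

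The conflict over the window applies to both arms alike, and the two operational sections agree with each other. It is a drafting fault and not a source of differential bias in itself.

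**Conclusion.** The point holds in limited form. Free choice of step device, a glucose app with optional alerts on the phone in one arm, a baseline taken before that app is in use, and no analysis by device together allow visit 2 steps to rise more in the RT-CGM arm without more walking.

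The direct mechanism reaches phone users at visit 2 only. For a day-84 visit it acts on about half the window. A reader might extend it to visit 3, but no RT-CGM is worn in that window and only a carried-over habit could act.

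The figure of 125 to 300 steps/day rests wholly on assumed true steps, phone share and carrying. It shows what is possible, not what is likely, and it would not justify calling an observed gain in steps spurious. A1C and the Aim 3 primary outcome (sugared beverages) are untouched.

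The contradiction between the Aim 3 statement and Sections H and K needs no assumption: staff cannot follow both. Taken together, this is a cheap improvement to one secondary outcome.

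**What to change.** - Make the supplied pedometer the default step source. Section K already provides for supplying one to every participant.
- Where a phone is used, keep the same device for that person in all three windows and record the device type at each visit.
- Add a sensitivity analysis of the between-arm step contrast restricted to pedometer users. Holding the same phone constant removes device shifts but not differential carrying, so the device rule alone is not enough.
- Reconcile the Aim 3 statement with Sections H and K so that one window, before or after visits 2 and 3, applies to both arms.

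The cost is a wording amendment and an instruction to coordinators. The downside is somewhat more missing step data from people who would rather use their phone.
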